 - RSVPreF3-specific IgG versus RSV A neutralizing antibody titer at each timepoint,
 - RSV A versus RSV B neutralizing antibody titer at Pre-vaccination and Day 91
 - RSVPreF3-specific IgG versus RSV-B neutralizing antibody titer at Pre-vaccination and Day 91

The same analysis will be performed on the fold increase post over pre-vaccination.

For each assay, values strictly below the cut-off and values strictly greater than the upper limit of quantification (ULOQ) will not be used for the scatter plots neither for the evaluation of the coefficients of correlation.

- The fold increase (post over pre-vaccination) of the RSVPreF3 IgG antibody concentrations versus the fold increase (post over pre-vaccination) of RSV-A and RSV B neutralizing antibody titers will also be displayed graphically by group using scatter plots.
- The hMPV neutralizing antibody titers will also be tested at Day 1 and Day 91, on all subjects in Part A and on a subset of 40 subjects per group in Part B. The following analysis will be performed for each hMPV subtypes (A1, B1, A2, B2):
 - Percentage of subjects above pre-defined threshold and their exact 95% CI will be tabulated.
 - GMTs and their 95% CI will be tabulated and represented graphically.
 - Geometric mean of ratios of antibody titer at post-vaccination time point (Day 91) over pre-vaccination (Day 1) will be tabulated with 95% CI.
 - Antibody titer will be displayed using reverse cumulative curves.
 - Distribution of the fold increase of the antibody titers (post- over pre-vaccination titers) will be tabulated.
 - Individual post-vaccination results (Day 91) versus pre-vaccination results (Day 1) will be plotted using scatter plots for the selected RSV formulation and the placebo group as a reference.

CONFIDENTIAL208851 (RSV OA=ADJ-002)
Statistical Analysis Plan Amendment 2**5.3.2.2. Within groups – Cell-mediated immune response**

Descriptive statistics of the cell-mediated immune response will be tabulated and displayed graphically using boxplots (min, Q1, median, Q3, max), by group and timepoint.

The RSVPreF3-specific CD4+/CD8+ T cell frequencies will be obtained by subtracting the background value to the antigen-induced value, and by setting to 1 all values less than or equal to zero for geometric mean calculation and graphical representation. Frequencies will be expressed as the number of cells per million of CD4+/CD8+ T cells.

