As described for humoral response, the differences between RSV groups will be evaluated using an ANCOVA model including the adjuvant content (AS01B, AS01E, Plain), the antigen dose (30, 60, 120 µg), the visit (Day 31, Day 91) and the age category (age at Dose 1: 60-69 or 70-80 years) as fixed effects, and the pre-vaccination log-transformed CD4 T cell frequency following induction and the post-vaccination log-transformed CD4 T cell frequency under background condition as covariates.

All interactions will also be tested and included in the model if significant.

The following model will be used to analyse the log-transformed ratio between induction and background frequencies, and provide estimates of the RSVPreF3-specific CD4+ T cell frequency relative to background frequency. *These estimates better represent the net effect of the vaccines over the CD4+ T cells frequency as the nuisance background frequency is subtracted from the induction frequency.*

$$Y_{ijk} - x_{ijk} = \mu_{jk} + \alpha_j \cdot y_{i0k} + \beta \cdot x_{ijk} + \varepsilon_{ijk}, \text{ with}$$

$$\hat{Y}_{jk} - x_{ijk} \Big|_{\bar{y}_0, \bar{x}} = \mu_{jk} + \alpha_j \cdot \bar{y}_0 + \beta \cdot \bar{x},$$

LS means conditional to \bar{y}_0 and \bar{x} , where:

i, j, k =subject i , visit j , group k ; \bar{y}_0 = mean log induction frequency at pre-vaccination,

\bar{x} = mean log background after vaccination.

Note: This analysis is assuming that the background is the same for all groups and all timepoints. This assumption will be checked during the analysis.

CONFIDENTIAL208851 (RSV OA=ADJ-002)
Statistical Analysis Plan Amendment 2

From that model, the least-squares means are then back-transformed into geometric means for the Induction / Background frequency ratio. The Background mean is then subtracted from the Induction mean and the fold-increase on that difference is calculated, as follows:

$$\hat{Z}_{jk} = 10^{\hat{Y}_{jk}} - 1 = \frac{10^{\hat{Y}_{jk}} - 10^{\bar{x}}}{10^{\bar{x}}}, \text{ and}$$

$$\text{Log}(\hat{W}_{jk}) = \text{Log}\left(\frac{\hat{Z}_{jk_2}}{\hat{Z}_{jk_1}}\right) = \text{Log}\left(\frac{10^{\hat{Y}_{jk_2}} - 10^{\bar{x}}}{10^{\hat{Y}_{jk_1}} - 10^{\bar{x}}}\right), \text{ where}$$

\hat{Z}_{jk} = mean increase from background to induction frequency relative to background frequency at visit j for treatment k , and

\hat{W}_{jk} = vaccine effect on the antigen specific frequency following adjustment for background frequency.

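### The CD4+ T-cell model for the RSV groups omits the measured Day 1 background; adding it would be a minor, nearly free gain in precision

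*SAP*

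**What the plan says.** SAP Section 5.3.2.2 defines the antigen-specific response: "The RSVPreF3-specific CD4+/CD8+ T cell frequencies will be obtained by subtracting the background value to the antigen-induced value". Each frequency reported for a sample therefore needs both a medium-only (background) and a peptide-stimulated (induction) result. Section 2 has the cell-mediated immunity sample drawn from all Part B subjects at Day 1.

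Section 5.3.2.3 sets out the inferential model for the RSV groups. The outcome is log induction minus log background at the same post-vaccination visit. The factors are adjuvant, antigen dose, visit and age category. The continuous covariates are "the pre-vaccination log-transformed CD4 T cell frequency following induction and the post-vaccination log-transformed CD4 T cell frequency under background condition as covariates". The equation has the same two terms, y_i0k and x_ijk. LS means are taken at the "mean log induction frequency at pre-vaccination" and the "mean log background after vaccination". The section treats background as something to be removed, describing the estimates as better "as the nuisance background frequency is subtracted from the induction frequency". It also notes: "This analysis is assuming that the background is the same for all groups and all timepoints", and says this will be checked.

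No Day 1 background term (x_i0k) appears. The footnotes of Template Tables 27 to 31 refer only to a generic pre-vaccination log titer or frequency.

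**The concern.** The model treats the two ends of the comparison differently. After vaccination, induction is corrected for the background of the same visit. Before vaccination, raw induction is used as it stands. By the SAP's own definition that value is specific response plus background, so as a measure of pre-existing RSVPreF3 memory it carries a component the plan itself calls a nuisance. The quantity that would help separate the two is already measured.

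What is at stake is precision. A baseline covariate that mixes memory with background predicts the post-vaccination response less well than the two components entered side by side. The confidence interval for the pooled adjuvant contrast on this secondary endpoint may then be somewhat wider than the data require.

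**Working it through.** **1. Is the term really absent?** The covariate sentence, the equation and the LS-means definitions agree with one another, and none contains x_i0k. The sentence on testing all interactions cannot supply a missing main effect. The equal-background note concerns the level of background across groups and visits; it does not remove variation within a subject between visits.

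**2. Is the baseline covariate a mixture?** Take three illustrative Day 1 splits of background plus specific frequency, per million: 50 + 350, 200 + 200 and 350 + 50. Each sums to 400, so each gives log10(400/1,000,000) = −3.398. The model sees three identical subjects.

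**3. What does it cost?** The SAP states no power or precision figure that depends on this covariate, so there is none to reproduce. The size was simulated.

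- From the SAP: about 70 + 30 = 100 subjects per group and three antigen doses per adjuvant family, hence 300 vs 300; the 0.5-cell offset; the log10 scale; outcome Y − x; covariates y_i0 and post-vaccination x.
- Assumed: Poisson counts on 200,000 CD4 cells; background 50 to 300 and baseline specific frequency 100 to 400 per million; post-vaccination control level 900 per million; true effect 0.2 log10; between-subject log10 SD 0.4 for the specific part; persistent and visit-to-visit background SDs each 0.15 to 0.3. Both wells of a visit share that visit's background level.
- Formula: excess variance of the planned model = (SE planned / SE with x_i0)² − 1.

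Selected results for the group coefficient:

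| Background / specific at Day 1 | Persistent / visit SD | SE planned | SE with x_i0 | Ratio | Excess variance |
|---|---|---|---|---|---|
| 50 / 400 | 0.3 / 0.15 | 0.0269 | 0.0269 | 1.0002 | 0.0% |
| 50 / 100 | 0.3 / 0.3 | 0.0286 | 0.0280 | 1.0240 | 4.9% |
| 150 / 200 | 0.3 / 0.3 | 0.0264 | 0.0253 | 1.0434 | 8.9% |
| 300 / 100 | 0.3 / 0.3 | 0.0257 | 0.0240 | 1.0724 | 15.0% |
| 300 / 100 | 0.15 / 0.3 | 0.0256 | 0.0238 | 1.0735 | 15.2% |

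The largest case is 1.0735² − 1 = 15.2% excess, or 1 − 1/1.152 = 13.2% as a reduction.

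The 300 / 100 row with SDs 0.3 / 0.3 shows the mechanism. Without y_i0 the SE is 0.0265. Day 1 induction alone removes 1 − (0.0257/0.0265)² = 5.9% of the variance; induction and background together remove 1 − (0.0240/0.0265)² = 18.0%.

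**4. Is there bias?** No. At 150 / 200 with SDs 0.3 / 0.3 the estimates are 0.1656 without and 0.1654 with x_i0. Under the null at 50 / 200 they are 0.0001 and 0.0002, with Monte Carlo SE 0.0007.

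**5. When does the gain vanish?** Further simulations, also 300 vs 300, used 150,000 cells. The figures are variance with x_i0 over variance without.

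- Run through to the delta-method variance of log10(W), with a shared run background, median background 30 to 250 and baseline specific frequency 30 to 200 per million, and run-to-run SD 0.1 to 0.25: 0.998, 0.958, 0.916, 0.917, 0.862 and 0.990.
- The same with unrelated backgrounds in the two wells: 0.997 to 1.001.
- No drift between visits, persistent SD 0.25, at 30/200, 100/100, 250/100 and 250/30 per million: 1.001, 1.000, 1.000 and 1.001.
- Drift SD 0.1 at 100/200: 0.993. Drift SD 0.25 with persistent SD 0.20: 0.995, 0.926, 0.870 and 0.944.

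**The case against.** The strongest reply is that this is a preference and not an error. The covariates are pre-specified and internally consistent, and almost any ANCOVA could carry one more prognostic covariate. That stands, and it is why the point is minor.

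The same-visit background x_ijk already absorbs a subject's persistent background. This also stands: without drift between visits the gain is nil, even when background far exceeds the specific response. Nothing in the SAP shows how much drift to expect. If the two wells' backgrounds were unrelated the gain would also vanish, though that would equally weaken the plan's own reason for adjusting for same-visit background.

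The added term is only a proxy. Log background entered linearly beside log induction does not reproduce induction minus background, and at low background it is noisy: 30 per million × 150,000 cells is about 4.5 expected cells. True, but it keeps the 0.5-cell offset and avoids taking logs of non-positive differences, and no simulated setting showed a material loss from it.

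The simulations used ordinary least squares at one visit, not the planned repeated-measures model, and covered only one two-group adjuvant contrast.

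A reader might infer that the CD4+ contrasts are biased or that type I error is inflated. The documents do not support that, because allocation is randomised and the omitted value is a baseline one. A reader might also extend the loss to the Placebo and antigen-dose comparisons. The covariate sentence at issue concerns differences between RSV groups, Section 5.3.2.3(a) describes the Placebo model separately, and neither consequence was simulated.

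**Conclusion.** The point holds as a minor improvement in precision. The planned CD4+ model is valid and unbiased, but its baseline covariate mixes specific memory with background although the Day 1 background is measured.

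On assumed inputs, adding that background changes the variance of the pooled adjuvant contrast by 0 to roughly 15%. At the upper end this is 13 to 14% as a reduction (ratio 0.862 gives 13.8%) and 15 to 16% as an excess (1/0.862 = 1.160). Confidence intervals are therefore at most about 7 to 8% wider than necessary (√1.160 = 1.077). The upper end needs background that varies between visits, is shared by both wells, and is at or above the baseline specific frequency.

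The SAP supplies none of the background level, specific level or variances behind this range. Section 6 makes all comparisons exploratory, and no stated power claim depends on this covariate.

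**What to change.** In Section 5.3.2.3, add the pre-vaccination log10 background frequency to the CD4+ RSV-group model, with the same 0.5-cell offset and a slope by visit as for y_i0k. Evaluate LS means at its overall mean. The back-transformation to Z and W can stay as written, still using the post-vaccination mean background. State in the CD4+ template footnotes which baseline frequencies are in the model. The same covariate may be used in the CD4+ Placebo comparison for consistency, without claiming a gain there. If the sponsor prefers raw induction alone, a sentence giving the reason and the clarified footnotes would be enough.

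The cost is one or two degrees of freedom against about 900 subjects (nine RSV groups × about 100), plus one program term and a few lines of text. No new data are needed. Subjects without a Day 1 background result would drop out of the model, but they would already lack a Day 1 specific frequency.

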5.3.1.3. Between groups evaluation (Part B only)

Statistical analyses will be performed to compare the 9 RSV investigational vaccine formulations in terms of RSV-A neutralizing antibody titers and RSVPreF3-specific CD4+ T-cells expressing at least 2 markers among IL-2, CD40L, TNF- α , IFN- γ .

The between-groups analysis will be performed using an ANCOVA model, in several steps as follows:

1. The 9 RSV formulations will be first compared to the Placebo in order to identify groups whose means are significantly higher from the mean of the Placebo group, in terms of RSV-A neutralizing antibody titers and RSVPreF3-specific CD4+ T-cells at Day 31 and Day 91 (One-sided alpha=2.5%, Dunnett's adjustment test for multiplicity).
2. The effect of the second vaccination will be evaluated by comparing the means one month post-Dose 2 (Day 91) and one month post-Dose 1 (Day 31), of the groups pooled according to their adjuvant content (AS01_B, AS01_E and Plain), in terms of RSVPreF3-specific CD4+ T-cells and RSV-A neutralizing antibody titers (One-sided alpha=2.5% for each superiority test: 2 doses > 1 dose).

Based on the results of this test, the next comparisons will be performed either at Day 91 or at Day 31.

3. Appropriate contrasts will be implemented to compare the RSV formulations as follows:
 - To demonstrate the adjuvant effect (on pooled groups according to their adjuvant content: AS01_B, AS01_E, Plain), by testing sequentially AS01_B and AS01_E versus Plain (One-sided alpha=2.5% for each superiority test: Adjuvant > Plain) in terms of RSVPreF3-specific CD4+ T-cells and RSV-A neutralizing antibodies and, if applicable, by comparing AS01_B vs AS01_E.
 - To demonstrate linearity of increase in immune response when increasing the antigen dose in each adjuvanted group in terms of RSV-A neutralizing antibody and/or RSVPreF3-specific CD4+ T-cells.
 - Further ANCOVA t-tests would demonstrate superiority of 120 μ g or 60 μ g, should a quadratic effect be demonstrated.

Similar exploratory comparisons might also be performed on the RSVPreF3 ELISA antibody concentrations if deemed necessary.

CONFIDENTIAL208851 (RSV OA=ADJ-002)
Statistical Analysis Plan Amendment 2**5.3.2. Additional considerations****5.3.2.1. Within groups – humoral immune response**

- Correlations between assays of the humoral response will be investigated using scatter plots generated on pooled RSV groups in Part B:

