The adjuvant effect will be tested sequentially as follow (One-sided alpha=2.5% for each superiority test):

- i. AS01B versus Plain
- ii. AS01E versus Plain
- iii. AS01B versus AS01E.

Geometric mean ratios and their 95% CIs will be computed for each comparison.

The same comparisons will also be performed by age category.

3. Antigen dose-response: test linear and quadratic effect of the antigen dose.

Depending on significance of those 2 effects, ANCOVA t-tests might be done to demonstrate superiority of 120 µg or 60 µg.

Geometric mean ratios and their 95% CIs will be computed for each pairwise comparison within each adjuvant content family (120 µg vs 60 µg, 120 µg vs 30 µg, 60 µg vs 30 µg for Plain, AS01E and AS01B groups).

Here is an example of SAS code that will be used:

```

PROC MIXED DATA=test;
  class Adj(1B, 1E, PL) Ag(30, 60, 120) visit(PD1, PD2) subject agecat;
  model log(titer) = Adj Ag visit Adj*Ag Adj*visit Ag*visit Adj*Ag*visit
  baseline baseline*visit agecat / DDFM=KR S outpm=pred_model cl;
  REPEATED visit / SUBJECT=subject type=unr group=Adj;
  /* test homogeneity of variances and consider different variance by
  adjuvant content if appropriate */

  LSMEANS Adj*visit /E slice=visit CL PDIFF ALPHA=0.05; /*option E to see
  coefficients assigned to each effect */
  LSMEANS Adj*visit /E slice=Adj CL PDIFF ALPHA=0.05;
  LSMEANS Adj*Ag*visit / slice=visit CL PDIFF ALPHA=0.05;

  /* contrasts to be added for each comparison of interest */
  QUIT;

```

CONFIDENTIAL208851 (RSV OA=ADJ-002)
Statistical Analysis Plan Amendment 2

The inferential analysis on the RSVPreF3-specific CD4+ T cells will be performed on the log-transformation frequency of the CD4+ T cells expressing at least 2 markers (background or induction) computed by adding an offset of 0.5 cells to the number of activated CD4+ T cells (Delta method, see below). These transformations are deemed appropriate for further inferential analyses provided the incidence of activated CD4+ T-cells is below 4%.

Considering:

$$X_{ijk} = \log\left(\frac{n_{Background}^{2+} + 0.5}{N_{Background}^{CD4}}\right), \text{ the log background frequency, and}$$

$$Y_{ijk} = \log\left(\frac{n_{Induction}^{2+} + 0.5}{N_{Induction}^{CD4}}\right), \text{ the log induction frequency}$$

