The test and the 95% CIs for treatment comparisons will be calculated according to the delta method on the log-transformed ratio of RSVPref3-specific frequency relative to the background frequency estimates.

For each comparison, the covariance matrix of the means is pre multiplied and post-multiplied by the vector of partial derivative to provide the variance of the contrast:

$$\text{Var}\left(\text{Log}_{10}\left(\frac{\hat{Z}_{jk_2}}{\hat{Z}_{jk_1}}\right)\right) = T\left(\nabla_{\hat{Y}_{jk_1}, \hat{Y}_{jk_2}}(\bullet)\right) \cdot \sum \cdot \nabla_{\hat{Y}_{jk_1}, \hat{Y}_{jk_2}}(\bullet)$$

Where

\sum is the covariance matrix, and

$$\nabla_{\hat{Y}_{jk_1}, \hat{Y}_{jk_2}}(\bullet) = \nabla_{\hat{Y}_{jk_1}, \hat{Y}_{jk_2}}\left(\text{Log}_{10}\left(\frac{\hat{Z}_{jk_2}}{\hat{Z}_{jk_1}}\right)\right) = \begin{pmatrix} -1 - \frac{1}{\hat{Z}_{jk_1}} \\ 1 + \frac{1}{\hat{Z}_{jk_2}} \end{pmatrix}$$

The $\text{Log}_{10}(W_{jk})$ confidence interval is calculated based on the T-student percentile using the degrees of freedom provided by the MIXED procedure for the difference of means under consideration (eg Y_{jk_2} and Y_{jk_1}) and the standard error calculated above.

$$\text{Log}_{10}\left(\text{LowerCI}(W_{jk})\right) = \text{Log}_{10}\left(\frac{\hat{Z}_{jk_2}}{\hat{Z}_{jk_1}}\right) - \text{TINV}(1 - \text{alpha}/2, df) \cdot \sqrt{\text{Var}\left(\text{Log}_{10}\left(\frac{\hat{Z}_{jk_2}}{\hat{Z}_{jk_1}}\right)\right)}$$

The confidence intervals are then back-transformed to the original units to provide the confidence intervals for W_{jk} . (Amendment 2 – 17 MAR 2020).

CONFIDENTIAL208851 (RSV OA=ADJ-002)
Statistical Analysis Plan Amendment 2**5.4. Analysis of safety and reactogenicity****5.4.1. Analysis of safety and reactogenicity planned in the protocol**

The percentage of subjects with at least one local AE (solicited and unsolicited), with at least one general AE (solicited and unsolicited) and with any AE during the 7-day or 30-day follow-up period will be tabulated with exact 95% confidence interval (CI) after each dose and overall. The same computations will be done for Grade 3 AEs, for any AEs considered related to vaccination, for Grade 3 AEs considered related to vaccination and for Grade 3 non-serious AEs.

The percentage of subjects with any AE (solicited and unsolicited) resulting in a medically attended visit during the 30-day follow-up period will also be tabulated after each dose and overall.

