Assay	Timepoint	RSV group	N	GM<T,F> ratio (RSV over Placebo)	Dunnett's 95% CI		Dunnett's p-value
					LL	UL	
<assay name>	<Day 31, Day 91>	30-PLAIN_B					
		60-PLAIN_B					
		120-PLAIN_B					
		30-AS01E_B					
		60-AS01E_B					
		120-AS01E_B					
		30-AS01B_B					
		60-AS01B_B					
		120-AS01B_B					

Short group label = long group label

N= Number of subjects with both pre- and post-vaccination results available

GM<T,F>= = Geometric mean antibody <titer, frequency> adjusted for covariates (ANCOVA model)

RSV Vaccine is considered superior to Placebo if one-sided p-value <0.025

Dunnett's 95% CI = 95% confidence interval based on Dunnett's adjustment, LL = lower limit, UL = upper limit

ANCOVA model on the log-transformed <titers, frequencies> with the pre-vaccination log-transformed

<titer,frequency> as covariate, and the treatment and age category as fixed effects

CONFIDENTIAL208851 (RSV OA=ADJ-002)
Statistical Analysis Plan Amendment 2**Template Table 28 Comparisons of the mean responses post dose 2 (Day 91) versus post dose 1 (Day 31) in terms of <RSV A Neutralizing antibody titers, RSVPreF3-specific CD4 T cells expressing at least 2 markers among IL-2, CD40L, TNFa, IFNg> on pooled groups according to adjuvant content (ANCOVA model) – Part B <Per Protocol set >**

Assay	RSV group	N	GM<T,F> ratio (D91/D31)	95% CI		p-value
				LL	UL	
<assay name>	PLAIN_B					
	AS01E_B					
	AS01B_B					

Short pooled group label = long pooled group label

N= Number of subjects with results available at both timepoints

GM<T,F> = Geometric mean antibody <titer, frequency> adjusted for covariates (ANCOVA model)

PII D91 is considered as significantly higher to PI D31 if one-sided p-value <0.025

95% CI = 95% confidence interval for the adjusted GMT (Ancova model: adjustment for covariates - pooled variance);

LL = lower limit, UL = upper limit

ANCOVA model on the log-transformed <titers, frequencies> with the pre-vaccination log-transformed

<titer,frequency> as covariate, and the adjuvant content, antigen dose and age category as fixed effects

Template Table 29 Comparisons of the RSV groups pooled according to their adjuvant content (Plain, AS01E, AS01B) in terms of <RSV A Neutralizing antibody titers, RSVPreF3-specific CD4 T cells expressing at least 2 markers among IL-2, CD40L, TNFa, IFNg> at Day 91 (ANCOVA model) - Part B <Per Protocol set>

		Group 1				Group 2				GM<T,F> ratio (Group 1 / Group 2)			

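### The CD4+ T-cell superiority test is a delta-method t on log10(Z2/Z1): very conservative, and sometimes not computable, when the comparator's specific response is close to background; whether it also governs the Placebo comparison is unclear

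*SAP*

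**What the plan says.** All references are to SAP Amendment 2.

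Section 5.3.2.3 models the log10 ratio of induction to background frequency and evaluates every LS mean at the same mean baseline and the same mean background. It converts each LS mean Y to Z = 10^Y - 1, defined as the "mean increase from background to induction frequency relative to background frequency at visit" j for treatment k. Two groups are compared through W = Z2/Z1, and both the test and the interval come from log10(W): "The test and the 95% CIs for treatment comparisons will be calculated according to the delta method on the log-transformed ratio". The variance uses the gradient (-1 - 1/Z1, 1 + 1/Z2), and the "confidence interval is calculated based on the T-student percentile using the degrees of freedom provided by the MIXED procedure".

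On scope, the text points two ways.
- The delta-method passage opens without excepting Placebo: "The inferential analysis on the RSVPreF3-specific CD4+ T cells will be performed on the log-transformation frequency of the CD4+ T cells". But it stands under heading b, Comparisons between RSV groups, and its model is introduced with "the differences between RSV groups will be evaluated using an ANCOVA model including the adjuvant content (AS01B, AS01E, Plain") and the antigen dose as factors.
- Section 5.3.1.3 requires a Placebo comparison for CD4+ T cells as well as for neutralizing titers: "The 9 RSV formulations will be first compared to the Placebo in order to identify groups whose means are significantly higher". Heading a of 5.3.2.3 gives that comparison an ANCOVA with Dunnett-adjusted LS means. Template Table 27 lists CD4+ frequencies, reports a Dunnett p-value and interval, and carries the rule "RSV Vaccine is considered superior to Placebo if one-sided p-value <0.025".

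Section 5.3.2.2 handles non-positive net frequencies "by setting to 1 all values less than or equal to zero for geometric mean calculation and graphical representation". No rule covers a non-positive Z in the inferential analysis.

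**The concern.** A superiority test should become stronger as the comparator gets weaker. This one does the reverse once the comparator is close to background. For small Z1 the estimate log10(Z2/Z1) grows only like -log10(Z1), while its standard error grows like 1/Z1, so the t statistic falls towards zero. At Z1 <= 0 the logarithm does not exist. The test is then largely asking whether the comparator's own response is precisely above zero, which is not the question posed.

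CD4+ T cells are one of the two responses used for the adjuvant, antigen-dose and second-dose comparisons, and for the Placebo screen. At stake are real differences reported as not shown, or a missing p-value, in comparisons against a weak comparator.

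**Working it through.** **Inputs from the SAP.** One-sided alpha of 2.5%; about 70 + 30 = 100 subjects per group; pools of three groups by adjuvant, so about 3 x 100 = 300 overall and 3 x 30 = 90 aged 70-80; a common background across groups.

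**Assumptions.** The SAP gives no CD4+ SD and no value of Z for any group, so both are assumed: log10 residual SD of 0.4 (range 0.3 to 0.6), Z as shown. LS means are treated as independent, so the figures do not cover the within-subject Day 91 versus Day 31 contrast. Critical values are 1.96 unadjusted and about 2.68 for Dunnett with nine groups against one. The SAP states no power or effect size here, so there is no figure of its own to reproduce.

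**Step 1: the variance formula.** d log10(10^Y - 1)/dY = 10^Y/(10^Y - 1) = 1 + 1/Z. The stated gradient is correct. The fault is in relying on this linearisation when Z is near zero.

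**Step 2: the null hypothesis.** Z = 10^Y - 1 increases with Y, and all LS means share one background. So Z2 > Z1 exactly when Y2 > Y1, and the contrast Y2 - Y1 tests the same null.

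**Step 3: one case by hand.** n = 100, SD 0.4, so each LS mean has SE s = 0.4/√100 = 0.04. Take Z1 = 0.1, Z2 = 1.
- SAP test: log10(1/0.1) = 1; SE = 0.04 x √(11² + 2²) = 0.447; t = 2.24.
- LS-mean contrast: log10(2) - log10(1.1) = 0.260; SE = 0.04 x √2 = 0.0566; t = 4.59.
- Chance that the estimated Z1 is <= 0: Φ(-0.0414/0.04), about 15%.

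**Step 4: behaviour as the comparator weakens** (n = 100, SD 0.4, Z2 = 3).

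| Z1 | t, SAP test | t, LS-mean contrast | not computable |
|---|---|---|---|
| 0.5 | 5.93 | 7.53 | 0% |
| 0.2 | 4.78 | 9.24 | 2.5% |
| 0.1 | 3.33 | 9.91 | 15% |
| 0.05 | 2.11 | 10.27 | 30% |
| 0.0001 | 0.01 | 10.64 | 50% |

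**Step 5: simulated power between RSV groups** (critical value 1.96, SD 0.4; non-computable results counted as no rejection).

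| n per arm | Z1 vs Z2 | LS-mean contrast | SAP test |
|---|---|---|---|
| 300 | 0.5 vs 1 | 96.9% | 96.7% |
| 300 | 0.2 vs 1 | 100% | 99.8% |
| 300 | 0.1 vs 1 | 100% | 89% |
| 100 | 1 vs 2 | 87.5% | 87.0% |
| 100 | 0.3 vs 2 | 100% | 98.9% |
| 100 | 0.2 vs 1 | 97.5% | 83% |
| 100 | 0.1 vs 1 | 99.6% | 57% |
| 90 | 0.2 vs 1 | 96% | 77% |

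Under the null at n = 100 with Z1 = Z2 = 0.2, the SAP test rejects about 0.01 to 0.02% of the time instead of 2.5%; at Z1 = Z2 = 0.5, about 1.2%.

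**Step 6: if the test were also used against Placebo** (critical value 2.68, n = 100, SD 0.4 unless stated).

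| Placebo Z vs vaccine Z | LS-mean contrast | SAP test |
|---|---|---|
| 0.3 vs 1 | 74% | 43% |
| 0.2 vs 1 | 89% | 38% |
| 0.1 vs 1 | 97% | 20% |
| 0.05 vs 2 | 100% | 36% |
| 0.1 vs 1, SD 0.3 | 100% | 59% |
| 0.2 vs 2, SD 0.5 | 99.8% | 68% |

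**The case against.** The strongest objection concerns scope. A reader might infer that an effective vaccine is liable to fail against Placebo under this plan. The document does not establish that. Heading a of 5.3.2.3 and Template Table 27 already describe a Dunnett-adjusted LS-mean ANCOVA for Placebo, which is close to the remedy proposed here. The delta-method model uses adjuvant and antigen dose as factors, and Placebo has no level in either. Its unadjusted Student-t interval also could not produce Template Table 27's Dunnett output. Against this, the opening sentence on CD4+ inference makes no exception, and the 0.5-cell offset and background handling are written out only there. The scope is therefore ambiguous, and the figures in Step 6 are conditional.

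Second, nothing in the SAP shows that any group mean lies near background. The rule in 5.3.2.2 concerns individual subtracted values in descriptive geometric means and graphs. Some subjects at or below zero does not put a group's LS mean there. This stands: every Z used here is assumed.

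Third, section 6 labels all comparisons exploratory, the error is conservative and so creates no false claim of superiority, and the planned LSMEANS statements would show the direct contrast anyway. These points limit the consequence. They do not make log10(W) a sound basis for the p-value, and the SAP names it as the test.

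Fourth, the present scheme keeps test and interval on one scale. That is a real advantage, and the fix gives it up.

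**Conclusion.** The point holds in a limited form. The CD4+ test in 5.3.2.3 is strongly conservative, loses power and can be undefined when the comparator's specific response is small relative to background: Z below roughly 0.3 at about 100 per group, or about 0.1 for pools of about 300, assuming a log10 SD of 0.4. Between RSV groups, where it clearly applies, that requires a weak comparator such as Plain in the 70-80 year stratum; otherwise the loss is negligible. Against Placebo the loss could be much larger, but only if the delta method is meant to apply there and Placebo does sit near background. The SAP settles neither. Because the comparisons are exploratory and the error is conservative, this is an inexpensive improvement and a needed clarification, not a threat to the trial's conclusions.

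**What to change.** In 5.3.2.3:

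1. State that all CD4+ superiority p-values (Template Tables 27 to 30) come from the LS-mean contrast of the log10 induction/background model, one-sided 2.5%, with Dunnett adjustment versus Placebo. Under the common background this tests the same null, Z2 = Z1. The sentence also settles which method governs the Placebo comparison.
2. Keep W = Z2/Z1 as the effect estimate, with a 95% CI obtained by simulating the LS means from their estimated covariance matrix.
3. Report the ratio or its upper limit as not estimable when the comparator's Z is not clearly above 0, and define that in advance, for example as more than 2.5% of simulated comparator values at or below zero.

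The cost is a few sentences and a few lines of SAS, since the planned LSMEANS statements already supply the contrasts between RSV groups and the Dunnett comparison. The p-value and the interval for W may occasionally disagree; a table footnote should say so.
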